9.3.3 Covariates

9.4 DATA SOURCES

An analysis based on anonymous claims data provided by two cooperating German sickness funds (planned: [REDACTED] + one additional sickness fund) covering the years 2013 - 2017 will be conducted. German claims data are a valid and often used source for health-economic analyses [5, 6, 7, 8, 9, 10, 11]. Validity of recording and coding can be evaluated as high in these databases. This is especially the case for any inpatient and prescription data because these data are directly relevant for reimbursement of hospitals/pharmacies by sickness funds. One of the main strengths of a claims data analysis are the use of an unselected large patient sample. This allows us to define cohorts, which are adequately powered to address the issues we are exploring.

For the claims data analysis, [REDACTED] will involve its university-affiliated partner, the [REDACTED] will close a contract with the cooperating sickness fund. This includes a detailed and mutually agreed list of a data extraction manual defining inclusion/exclusion criteria as well as all variables and formats to be used. Moreover, it outlines which data protection measures need to be implemented by [REDACTED]. The sickness funds will participate in the Steering Board of the study as well as being a co-author of all future publications of study results.

For a subsample of patients, disease management program (DMP) data might be available. These provide disease specifics such as FEV₁ values, specifics of prescribed therapy, and exacerbation frequency and severity. Respective subsamples with availability of DMP data have been defined.

9.5 STUDY SIZE

Based on an initial feasibility assessment/previous study done by [REDACTED] based on the [REDACTED] dataset only, **N>40,000** incident COPD patients meeting above inclusion/exclusion criteria can be expected. Among them, about 26,000 (~65%) received at least one prescription of a long-acting bronchodilator in the 12 months follow-up period. Percentage of incident patients with at least one DMP documentation (providing more detailed information for additional analysis) is about 30%.

9.6 DATA MANAGEMENT

[REDACTED] will be responsible for data management, including quality checking of the data. Especially, the confidentiality of records that could identify patients within the database must be protected, respecting the privacy and confidentiality rules in accordance with the applicable regulatory requirement(s). Confidentiality is ensured by pseudonymizing of the dataset. A data protection plan will be in place ensuring that no data will be transferred to third parties and that access to data will be granted only to the core project team. Please note that no data but only aggregated study results will be transferred to the steering board of this study. The data protection plan is based on applicable German law; it is available on request.

(in German language). Initial data processing will be undertaken using Microsoft SQL Server 2014 later statistical analyses will be done using SPSS version 20, MS-Excel version 2016, and STATA version 14.1.

9.7 DATA ANALYSIS

9.7.1 Main analysis

Generally, for all analyses specific samples will be used; these have been defined further above. Mainly, descriptive statistics will be applied in this study. Descriptive analysis of the data will be performed using summary statistics for continuous and categorical data. Continuous data will be described by the number of non-missing values, median, mean, range, standard deviation and 95% confidence intervals (CIs). Frequency tables will be generated for categorical data. Selected continuous variables will be categorized in a clinically meaningful way.

For rates/frequencies related to time periods, that might vary between the patients (e.g. shorter follow-up period due to death), respective numbers will be reported per patient-year (PY).

Furthermore, time-to-event analyses (Kaplan-Meier curves) will be conducted whenever applicable and appropriate. Especially, for the ██████████ KM curves will be evaluated.

Comparisons for categorical variables will be conducted using either Chi-square tests or Fisher's exact test (when the values in any of the cells of a contingency table are below 5). For continuous variables, statistical comparisons will be conducted using t-test or a suitable non-parametric test (for variables with skewed distribution).

The main analyses planned are summarized in Table 5.

Table 4 Overview of main planned analyses

Endpoint/study objective	Time period	Main reporting/analyses
PRIMARY: Description of drug treatment of incident COPD patients	Different follow-up periods since index date	Descriptive statistics (categorical variables: frequencies/percentages; continuous variables: mean, SD, median, ranges and 95% CIs) Comparisons for categorical variables: either Chi-square tests or Fisher's exact test; Comparison for continuous variables: t-test or a suitable non-parametric test Analysis of time to escalation therapy (therapy including ICS) using KM methodology

Table 4 (cont'd)

Overview of main planned analyses

Comparative analysis	Objectives 16, 17, 18	Design F	Statistical Methods F	Sample Size F	Timeline F
Surveillance analysis	Objectives 19, 20, 21	Design G	Statistical Methods G	Sample Size G	Timeline G
Adaptive analysis	Objectives 22, 23, 24	Design H	Statistical Methods H	Sample Size H	Timeline H
Final analysis	Objectives 25, 26, 27	Design I	Statistical Methods I	Sample Size I	Timeline I

Table 4 (cont'd)	Overview of main planned analyses
------------------	-----------------------------------

9.8 QUALITY CONTROL

The study data management will adhere to pre-defined process guidelines which mainly consist of the following elements:

[figure not shown]
- Internal staff engaged in this study will be trained; training will be documented.
- A data validation based on a 100% computer-assisted checking of variables/values (MIN, MAX, MEAN, MEDIAN, cross-checking of variables etc.) will be done after data delivery.

Study design and study conduct will be in line with legal and regulatory requirements, as well as with scientific purpose, value and rigor and follow generally accepted research practices such as *Good Pharmacoepidemiology Practices* (GPP) issued by the International Society for Pharmacoepidemiology (ISPE), the International Society for Pharmacoeconomics and Outcomes Research (ISPOR) guidelines, Pharmaceutical Research and Manufacturers Association (PhRMA) guidelines and similar rules.

9.9 LIMITATIONS OF THE RESEARCH METHODS

The main limitation of this claims data analysis is the limited availability of clinical information (clinical parameters, prescribed dosages, reasons for prescribing specific agents etc.). Information available in claims data is limited to parameters, which are generally relevant for reimbursement purposes. Clinical parameters will be only available for patients who participate in a DMP, whereas the validity and frequency of these documentations as well as the time of first documentation for incident COPD patients need to be checked. For a substantial part of the patients, these data might not be valid/available.

In addition to that, the available claims dataset will be a regional dataset, which probably covers only the regions of [REDACTED].

9.10 OTHER ASPECTS

Not applicable

9.11 SUBJECTS

In this claims data analysis, patient selection takes place according to pre-defined inclusion criteria as outlined above. The overall sample of COPD-incident patients will be divided into subgroups, according to minimum follow-up periods and availability of DMP data. The assumptions/criteria for the assignment of each patient to the respective subgroups was described above.

9.11.1 Cases

Not applicable

9.11.2 Controls

Not applicable

9.12 BIAS

By nature of the dataset, there does not exist any study site/patient selection bias. As [REDACTED] insures selection of persons from [REDACTED] only, a regional bias might exist due to the fact that only two specific regions of Germany will be covered. Further only patients continuously insured over the study period within the [REDACTED] will be included in the analysis, as this restriction is necessary for not considering patients multiple times. Thus, a potential selection bias is possible and the extent of the resulting effects will be estimated by describing the patients who were not continuously insured. Moreover, patients insured by the cooperating sickness funds may not be representative of the German COPD patients in terms of patient demographics. However, it is planned to involve another sickness fund in this study and thus, to cover another region of Germany. Furthermore, due to uniform treatment rules treatment of patients will not significantly differ from other regions.

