Research question and objectives:	
A. Description of the real-life drug treatment of patients with incident COPD, including description of treatment sequence/escalation in the first 12/24/36 months after incident diagnosis
 
B. Comparison of initial drug treatment of incident COPD patients with two versions of German treatment guidelines (2012/2018)
 
C. Description of exacerbation frequency (severe exacerbations associated with an inpatient hospitalization) of incident COPD patients in the first 12/24/36 months after incident diagnosis
 
D. Description of health-care resource use (HCRU; including use of oxygen therapy) and direct treatment cost of incident COPD patients in the first 12/24/36 months after incident diagnosis
		
Study design:	
A retrospective analysis will be done based on a claims dataset delivered by a German sickness fund (so far, a cooperation with [REDACTED] [REDACTED] (approximately 3.2 million insured persons) is planned; a second sickness fund might be included as well). The dataset will cover the period 01/01/2013-30/06/2018², and will only include patients who were continuously insured within the sickness fund between the entire period (death is the only exception)³. In selected analyses, incident COPD patients will be observed for an exact follow-up period of 12 months (in subgroup analyses: 24 and 36 months); censoring of patients will only be done in case a patient died during the respective follow-up period.
		

² If more data will be available until time of analysis start, further quarters (from 2018) will be included into the analysis. The Steering Board of the study will discuss whether it is meaningful to include additional data from 2010/2011/2012 taking into account that a ministry approval would be necessary in that case.

³ Continuous insurance is necessary, to not accidentally include patients twice in case they left the sickness fund intermediately and went back later on and are included within the dataset with two different pseudo numbers.

Name of company: Boehringer Ingelheim			
Name of finished medicinal product: COPD medication of any type			
Name of active ingredient: COPD medication of any type, ATC code R03			
Protocol date: 16 Oct 2019	Study number: 1237-0092	Version/Revision: 1.0	Version/Revision date: Not applicable

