9.2 SETTING

An anonymized dataset from the cooperating sickness funds, which includes all patients with at least one COPD diagnosis, who were insured by this sickness funds for the entire period (01/01/2013 - 30/06/2018) will be available.

A patient will be confirmed as being COPD-incident if specialists documented at least two confirmed outpatient COPD diagnoses (ICD J44.-) and/or at least one inpatient COPD diagnosis (ICD J44.-), without such diagnoses in the previous 12 months and without any COPD prescription in the previous 12 months (Suppl. Table 2).

Specific inclusion criteria can be described as follows:

- All patients should have been covered by the sickness fund for the entire period (01/01/2013-30/06/2018) or, in case a patient deceased after index date, for the time until death
- A patient will be included as an incident COPD patient if either a hospital documented at least one COPD diagnosis (ICD-10 J44.-) or a specialist (pneumologist) documented at least two confirmed COPD diagnoses (above ICD-10 code) in two different quarters; the first of the above diagnoses is defined as index diagnosis; inclusion period is defined as lasting from 01/01/2014 until 30/06/2017

- Patients should not have received any COPD diagnosis (ICD-10 J44.-) or any COPD-associated medication (Suppl. Table 2)⁹ in the 12 months pre-index period
- Patient should have, at date of incident COPD diagnosis (index date), an age of at least 40 years

Patients who received at least one confirmed inpatient asthma diagnosis or two confirmed outpatient diagnoses of asthma (ICD-10: J45.-) by pneumologists after the incident COPD diagnosis (index diagnosis) will be separately observed.

Based on these inclusion/exclusion criteria, the following data sets will be analyzed (Figure 3)¹⁰:

- COPD-FULL DATA: All incident COPD patients with a follow-up of up to 54 months
- COPD-12: All incident COPD patients with a follow-up¹¹ of 12 months since index date
- COPD-24: All incident COPD patients with a follow-up of 24 months since index date
- COPD-36: All incident COPD patients with a follow-up of 36 months since index date
- COPD DMP-FULL DATA: All incident COPD patients with available DMP data (at least one entry during 3 months after index date¹²) and a follow-up of up to 54 months.
- COPD DMP-12: All incident COPD patients with available DMP data (at least one entry during 3 months after index date) and a follow-up of 12 months since index date

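### Continuous insurance to 30/06/2018 selects patients on future cover, drops leavers but keeps deaths, and is not needed to prevent double counting

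*Combined protocol and SAP*

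**What the plan says.** The Abstract (study design) says the dataset "will only include patients who were continuously insured within the sickness fund between the entire period (death is the only exception"). Section 9.2 makes this an inclusion criterion, "All patients should have been covered by the sickness fund for the entire period (01/01/2013-30/06/2018"), and exempts deaths: "or, in case a patient deceased after index date, for the time until death". The start and end dates do not move with the index date, although the "inclusion period is defined as lasting from 01/01/2014 until 30/06/2017".

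The only reason given is double counting. Footnote 3 of the Abstract states: "Continuous insurance is necessary, to not accidentally include patients twice in case they left the sickness fund intermediately and went back later on", which could leave one person under two pseudonyms. Section 9.12 repeats that reason, "as this restriction is necessary for not considering patients multiple times".

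The Abstract and section 9.1 allow censoring only at death, so a patient who leaves the fund is excluded, not censored. Section 9.12 concedes that selection bias is possible and says "the extent of the resulting effects will be estimated by describing the patients who were not continuously insured". Footnote 5 of the Abstract adds an attrition chart. Section 9.2, however, describes an extract that holds only persons insured for the entire period.

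**The concern.** Eligibility should be settled by what is known at the index date. Here it also depends on whether the patient stays with the fund for one to four and a half years afterwards. Someone indexed on 01/01/2014 must stay 54 months to enter even the 12-month analysis, which is 42 months beyond the window being analysed. Someone indexed on 30/06/2017 needs only 12.

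Because deaths are exempt and leavers are deleted, the sample holds too many deaths relative to survivors, more so for early index dates. Death shortens follow-up and may bring resource use near the end of life. The selection can therefore reach the per-patient-year figures for exacerbations, resource use and cost, and the Kaplan-Meier analyses on the full sample.

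**Working it through.** **1. The plan's own figure.** From 01/01/2014 to 30/06/2018 is 4 × 12 + 6 = 54 months, which matches the maximum follow-up in section 9.1. The shortest required future cover is 30/06/2017 to 30/06/2018, or 12 months.

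**2. Is cover after index needed to avoid duplicates?** A person who leaves and returns has a second record that starts after 01/01/2013. That record fails a requirement of continuous cover from 01/01/2013 to index, whatever happens later. At most one record per person qualifies, so cover after index removes no further duplicates.

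An illustrative simulation agrees (4% per year leaving, no deaths). There were 0 duplicates under the plan's rule and 0 under cover to index, while the share of persons kept rose from 80% to 90%. A 12-month look-back alone, without the 01/01/2013 start, gave about 2 duplicates per 10,000, so the start date should stay.

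**3. Size of the selection.** Inputs from the documents are the index period, the data end and the exemption for deaths. Assumed inputs are constant yearly rates d (death) and l (leaving), independent of each other, and index dates uniform over the inclusion period. With T years from index to 30/06/2018 (1 to 4.5) and h = d + l:

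- Kept(T) = d/h + (l/h) × exp(−hT)
- Deaths seen within 12 months = (d/h) × (1 − exp(−h))
- Observed 12-month risk = deaths seen ÷ Kept; true risk = 1 − exp(−d)

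Example with d = 0.08, l = 0.04, h = 0.12:

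- True risk: 1 − exp(−0.08) = 7.7%.
- Deaths seen: 0.6667 × (1 − 0.8869) = 0.0754.
- Mean of exp(−0.12T) over T from 1 to 4.5: (0.8869 − 0.5827) ÷ (0.12 × 3.5) = 0.724. Mean kept: 0.6667 + 0.3333 × 0.724 = 0.908.
- Pooled COPD-12 risk: 0.0754 ÷ 0.908 = 8.3%, a factor of 1.08.
- January 2014 index: kept 0.861, risk 8.8%, a factor of 1.14.
- June 2017 index: kept 0.962, risk 7.8%, a factor of 1.02.

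Over l = 2-6% and d = 4-12% per year:

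| Index dates | Patients dropped | 12-month death risk overstated by |
|---|---|---|
| All (COPD-12) | 4-14% | 4-13% |
| January 2014 | 7-22% | 6-24% |
| June 2017 | 2-6% | 1-3% |

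**4. A named outcome.** Assume 20% high-risk patients (death 0.25 per year, 0.6 severe exacerbations per patient-year) and 80% low-risk patients (0.04 and 0.1). The true 12-month rate is 0.192 per patient-year. If both groups leave at the same 2-6% per year, the selected sample gives 0.193-0.194. If low-risk patients leave at 6% and high-risk at 2%, it gives 0.201, about 5% too high.

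**The case against.** The strongest reply is that the harm is modest and already acknowledged. Mortality is not among the visible objectives; date of death is collected for censoring and time-to-event analyses. Exacerbations per patient-year barely move when leaving is unrelated to risk, and no effect on treatment patterns (the primary outcome) or on guideline percentages has been shown. Section 9.12 names the possible bias, promises a description of those excluded, and an attrition chart is planned. All of this stands and limits the weight of the point. But a description or a chart discloses the selection without correcting any estimate. It may not even be possible if the extract holds only persons insured throughout.

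A reader might infer that death risk is overstated by up to 24% across the study. That figure belongs to the earliest index dates at the highest leaving rate, and the visible plan reports no such group alone. A reader might also infer that the 12-, 24- and 36-month results cannot be compared. The longer samples do draw on earlier index dates, which carry heavier selection. However, a given patient faces the same cover rule in every sample, and the comparison of yearly costs is made within COPD-36.

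**Conclusion.** The rule conditions on future insurance, treats leavers and deaths asymmetrically, and goes beyond what its stated purpose requires. Those three statements follow from the text and need no assumed rates. The size does: about 4-13% relative overstatement of pooled 12-month death risk in COPD-12, under constant and independent rates of 2-6% leaving and 4-12% dying per year and uniform index dates. For the named outcomes the effect is probably small. It could reach a few percent if lower-risk patients leave more often, which the plan as written could not check without leavers' data. The documents do not support a claim that the primary treatment description is materially wrong. The change is worth making because the restriction serves no purpose after index and a less biased alternative is available at little cost.

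**What to change.** - Require continuous cover from 01/01/2013 to the index date only, in the Abstract and section 9.2.
- In all samples, follow each patient to the earliest of leaving the fund, death, the end of the 12/24/36-month window or 30/06/2018. Censor at leaving, and amend the statements in the Abstract and section 9.1 that censor only at death.
- Define COPD-12/24/36 by an index date at least 12/24/36 months before data end, not by future cover. Requiring cover or death to the end of each window would still drop leavers and keep deaths. At 4% leaving and 8% dying per year, 36-month death risk in COPD-36 (true 21.3%) is overstated by 7.4% under the plan and still by 5.0% under that halfway rule.
- Report Kaplan-Meier and per-patient-year estimates with this censoring, and keep the fully insured sample as a sensitivity analysis.
- Reconcile section 9.2 (only persons insured throughout are delivered) with section 9.12 (leavers will be described), so that leavers are in the extract. Remove the opening statement of section 9.12 that no patient selection bias exists.

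The cost is a wider extract, which the funds must approve but which section 9.12 already needs, and some follow-up censored early. Simple percentages over a fixed window will need a stated rule for patients censored within it. Censoring at leaving also assumes that leaving is unrelated to outcome; comparing leavers with stayers at baseline would help to judge this.

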10. PROTECTION OF HUMAN SUBJECTS

In this study, anonymous data only will be analyzed. Patient/physician names will remain anonymous at any time. All data will be collected and processed with adequate precautions to ensure confidentiality and compliance with applicable data privacy protection laws and regulations.

10.1 PRINCIPLES OF GOOD RESEARCH PRACTICE

The guidelines of Good Clinical Practice developed by the International Council for Harmonization of Technical Requirements for Pharmaceuticals for Human Use (ICH-GCP guidelines) will be followed whenever applicable for this cross-sectional patients' survey.

10.2 PATIENT INFORMATION AND CONSENT

Generally, no informed consent (IC) is needed for this claims data analysis.

10.3 INDEPENDENT ETHICS COMMITTEE (IEC)

The study protocol will be approved by a Scientific Committee, consisting of external experts, the cooperating sickness funds, BI, and [REDACTED]. Due to the anonymous nature of the data, no ethical approval is needed.

10.4 CONFIDENTIALITY

BI as well as all investigators ensure adherence to applicable data privacy protection regulation. Data are transferred in encoded / anonymous form only. The entire documentation made available to BI does not contain any data, which, on its own account or in conjunction with other freely available data, can be used to re-identify natural persons. The investigators are obligated to ensure that no documents contain such data.

All records identifying the subject will be kept confidential and will not be made publicly available. Study findings stored on a computer will be stored in accordance with local data protection laws.

11. MANAGEMENT AND REPORTING OF ADVERSE EVENTS/ADVERSE REACTIONS

Not applicable based on secondary use of data without any potential that any employee of BI or agent working on behalf of BI will access individually identifiable patient data.

